## 10.5 Data and Safety Monitoring

If at any time within a given dose cohort:

- a) Three or more participants experience a Grade  $\geq 3$  AE related to study treatment ([section 10.2.1.1](#)) (as judged by the core team, blinded to treatment arm); or
- b) Two or more participants experienced an irAE (not including an infusion reaction AE) ([see section 10.4.1B](#)) that is related to study treatment (as judged by the core team, blinded to treatment arm); or
- c) One or more participants experience a Grade 4 clinical AE or death and related to study treatment (as judged by the core team, blinded to treatment arm);

then enrollment into the study and treatment infusions will be temporarily suspended and the SMC, unblinded to treatment assignment, will be asked to review all safety data; review the relation to study treatment of the event(s) thought by the blinded core team to be a primary safety outcome; and recommend how the study should proceed with respect to resuming enrollment, continuing study treatment and dose escalation.

## 10.6 Analyses

### 10.6.1 Primary Analyses

For the primary safety analysis, AEs attributed to study treatment ([see section 10.2.1.1](#)) will be described separately for the treatment arm of each dose cohort, and for the combined placebo arms. All participants who have been exposed to the study treatment/placebo will be included in this analysis. As supplemental/secondary analyses, all other reported AEs will be summarized for the treatment arm of each dose cohort, and combined placebo arm.

### 10.6.2 Secondary Analyses

For the HIV-1-specific CD8+ T cell efficacy outcome ([section 10.2.2.1](#)), post-treatment changes will be evaluated, comparing measurements at baseline (averaging the pre-treatment measures) to an average of post-treatment measurements through week 12, jointly analyzing the actively treated participants from all dose cohorts using the paired t-test. As supplemental analyses, the

same methods will separately analyze each dose cohort. The rationale to average over multiple post-treatment timepoints is that the timing and dynamics of treatment-induced immunologic (or virologic) effects is not known; the average of multiple time points aims to capture both early effects that may wane (for example, as seen in one of the immunologic responders to a single-dose of the anti-PD-L1 antibody [26]; or, for example, a response that only appears following the second infusion). Graphical approaches will display the means at each visit and mean changes from baseline to each follow-up visit (and separately to the average of weeks 2-6 and to weeks 8-12), by dose cohort and separately for the placebo participants. Longitudinal participant-specific plots will also be presented for each treatment dose and for the placebo participants.

Because the aim of this phase I/II study is to investigate the biologic effects of the treatment (anti-PD-1 antibody cemiplimab), efficacy analyses will be “as-treated” and also, to maximize the ability to identify treatment effects, efficacy analyses will be based only on participants who completed  $\geq 90\%$  of both study treatment infusions. In addition, if any participant interrupts cART for more than 7 consecutive days during the study, only measurements prior to cART interruption will be used in efficacy analyses.

Analyses of other immunologic and virologic measures will parallel the efficacy analyses as outlined above. For example, cell-associated HIV-1 RNA levels will be compared pre-treatment to post-treatment using paired t-tests separately by dose group (and for the combined treated participants) and for the placebo participants. Virologic measures such as cell-associated HIV-1 RNA will be log-transformed prior to analyses. Because low-level viremia as measured by SCA is anticipated to be below assay limit in a substantial fraction (~50%) of participants, binary (GEE) or censored-data [64] longitudinal analysis approaches are planned to assess treatment effects on SCA.

Descriptive summaries, by dose group, will be presented for the estimated PK parameters (see [section 11.0](#)). Graphical approaches will display concentration curves over time, as well as RO over time.

Designated staff at identified laboratories may be unblinded prior to database lock to facilitate bioanalytical analyses of pharmacokinetic samples and ex vivo immunogenicity studies.

The timing of treatment effects on immunologic and virologic outcome measures will be investigated by identifying, for each measure, the post-treatment timepoint with the greatest magnitude change from baseline. It is also of interest to evaluate whether there is evidence that the second dose of treatment further “boosts” responses following the first dose. For this reason, samples are collected at a comparable schedule following the first and second doses.

The associations between ex vivo HIV-specific T-cell responses following cemiplimab exposure (based on pre-treatment samples) and in vivo HIV-specific immune responses to treatment will be evaluated using Spearman correlations. Bioinformatics approaches will be used to evaluate changes in gene expression profiles before versus after treatment.

Regression models, graphical displays and correlation analyses will investigate dose-response relationships with respect to immunologic and virologic changes after treatment across the dose groups, and in relation to PK parameters estimated as outlined in [section 11.0](#).

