Multiple data sets support the dose panels selected for examination in this study. First, cemiplimab is an IgG4 subtype antibody and therefore is not capable of inducing antibody-dependent cytotoxicity or complement-dependent cytotoxicity cells. In addition, incubation of cemiplimab in blood samples from healthy human donors ex vivo did not result in any significant cytokine secretion and is thus not expected to independently promote T-cell activation. Given the need to establish safety in a different patient population from those patients previously tested (advanced malignancies), an initial dose of 0.3 mg/kg was selected with dose escalation to a top dose of 3 mg/kg based on interim review of safety during the protocol.

The initial dose selected to assess safety in this population is 0.3 mg/kg dose of cemiplimab, which is lower than that commonly administered in oncology studies. A dose lower than that with confirmed efficacy related to tumor stabilization or response in the oncology studies with cemiplimab was felt to be warranted, given this is the first study of an anti-PD-1 mAb in otherwise healthy, HIV-infected participants. Further, the 0.3 mg/kg cohort is important to help clearly define PK and RO in HIV-infected individuals, in addition to safety.

The dose of 1 mg/kg was selected based on prior use in the oncology studies described above with multiple doses of cemiplimab. As immunologic and virologic responses might be anticipated at the 1 mg/kg dose, data in this cohort will provide critical information for the lower dose response curve and the safety profile in the study population. The 1 mg/kg dose also provides a conservative margin of safety with a dose escalation of 3.3-fold (0.3 to 1 mg/kg).

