#### 10.4.2 Efficacy

For the secondary outcome measure of efficacy, statistical power is described for the paired t-test which will be used (two-sided, alpha=0.05), testing that CD8+ T cell responses ([10.2.2.1](#)) increase pre- to post-treatment among the active-treated study participants. The key assumption is that CD8+ T cell responses would be stable (mean change of zero) without intervention (i.e., with continued cART). Because estimates of the anticipated standard deviation (SD) of the change are not available, power is described in terms of SD units. With 11 evaluable treated participants in a dose group (allowing for one unevaluable, e.g., due to issues with the sample or assay), power is >80% to detect a treatment effect in a dose group if the mean change is at least 0.94 SD units; this

corresponds under assumed normality to a probability of 0.83 or larger that a participant would have an observed increase in CD8+ T cell responses after treatment (the null hypothesis is that the probability is 0.5, corresponding to zero mean change). Combining the three dose groups (n=33), power is >80% to detect a treatment effect of 0.504 SD units, corresponding to a probability of 0.69 or larger that a participant would have an observed increase in CD8+ T cell responses after treatment.

Adjustments for separate statistical testing in each of the dose cohorts have not been incorporated into power calculations for this study.

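### The main CD8+ efficacy test pools three dose cohorts without a dose term, and 10.4.2 does not say which SD its 0.504 is measured in; a cohort-stratified error term would protect power cheaply.

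*Protocol*

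**What the plan says.** Section 10.6.2 compares the pre-treatment average with the average of post-treatment values through week 12, "jointly analyzing the actively treated participants from all dose cohorts using the paired t-test". The same test in each cohort separately is supplemental. Section 10.6.2 also plans regression and correlation analyses of dose-response.

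Section 10.4.2 powers the test at two-sided 5%. For a single dose, with 11 of 12 evaluable, "power is >80% to detect a treatment effect in a dose group if the mean change is at least 0.94 SD units". For the pooled test: "Combining the three dose groups (n=33), power is >80% to detect a treatment effect of 0.504 SD units". It equates that effect with a chance of at least 0.69 that a given participant's response rises. On the unit it says: "Because estimates of the anticipated standard deviation (SD) of the change are not available, power is described in terms of SD units". It does not discuss effects that differ by dose.

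The CD8+ outcome is secondary; the primary outcome is safety (10.2). On expected activity, the Dose Rationale in Section 2.2 places 0.3 mg/kg below the doses with confirmed tumour efficacy and says of the middle dose: "As immunologic and virologic responses might be anticipated at the 1 mg/kg dose". It also reports no clear dose response above 1 mg/kg in oncology.

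**The concern.** A paired t-test on all 33 changes is a one-sample t-test whose error is the SD of all 33 values about their common mean. If the three doses have different mean changes, that SD contains the spread between doses as well as the variation between participants on the same dose. Cohort is a known design factor and could be taken out of the error with data already collected. Section 10.6.2 says its efficacy analyses are meant to maximise the chance of identifying treatment effects, and a pooled error term works slightly against that aim. At stake is some power for the main efficacy test. Type I error is not at stake, because with no effect at any dose the pooled test holds 5%.

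**Working it through.** **Inputs (10.4.2, 10.6.2).** Two-sided alpha 0.05; 11 evaluable per dose, 33 in all; detectable effects 0.94 SD (one dose) and 0.504 SD (pooled). The protocol gives no SD and no effect by dose, so the dose patterns below are assumptions.

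**Step 1: the plan's own figures.** Power of a paired t-test from the noncentral t, with df = n − 1 and noncentrality d√n:
- n = 33, d = 0.504: noncentrality 0.504 × √33 = 2.895, power 80.2%.
- n = 11, d = 0.94: noncentrality 0.94 × √11 = 3.118, power 80.2%.
- Probability of an increase: Φ(0.504) = 0.69 and Φ(0.94) = 0.83.

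All match 10.4.2.

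**Step 2: how dose differences enter the error.** With within-dose SD 1 and cohort means μ₁, μ₂, μ₃, the expected pooled variance is 1 + (33/32) × V, where V is the mean squared deviation of the three means from their average. For (0, 0.504, 1.008): V = (0.504² + 0 + 0.504²)/3 = 0.1693; 1 + 1.03125 × 0.1693 = 1.1746; its square root is 1.084, so the SD rises by 8%.

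**Step 3: power at the same average change, 0.504 within-dose SD.** Simulation with 400,000 trials per pattern and 11 per cohort. The pooled t-test (32 df) is set against a test of the same mean using the within-cohort variance (30 df).

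| Mean change at 0.3, 1, 3 mg/kg | Pooled SD | Pooled test | Stratified test |
|---|---|---|---|
| 0.504, 0.504, 0.504 | 1.000 | 80.2% | 80.1% |
| 0.252, 0.504, 0.756 | 1.022 | 78.9% | 80.0% |
| 0, 0.756, 0.756 | 1.063 | 76.3% | 79.9% |
| 0, 0.504, 1.008 | 1.084 | 75.2% | 80.1% |
| 0, 0, 1.512 | 1.234 | 65.0% | 80.0% |

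The exact value for the stratified test at 0.504 with 30 df is 80.0%, so the cost when doses are equal is 80.2 − 80.0 = 0.2 points. With no effect at any dose both tests reject in about 5% of trials.

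**Step 4: the other reading of the SD.** If 0.504 is in units of the total SD of the pooled changes, the spread between doses is already in the unit. Holding the total standardised effect at 0.504, the pooled test has 82.2% power when the means stand as 0:1:2 and 87.8% when they stand as 0:0:1. On this reading the stated figure survives unequal doses.

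**Step 5: dilution.** If the active doses reach only 0.504 within-dose SD and the others do nothing, the average itself falls.
- (0, 0.504, 0.504), average 0.336: pooled 44.1%, stratified 46.2%.
- (0, 0, 0.504), average 0.168: pooled 14.2%, stratified 15.4%.

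Nearly all of this loss comes from the smaller average, and stratification does not repair it.

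**Step 6: the planned per-cohort tests (n = 11, noncentral t).** Power is 99.4% at 1.512 SD, 85% at 1.008 SD and 62% at 0.756 SD.

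**The case against.** Three stronger readings are tempting, and the protocol does not support them.

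- A reader might infer that the stated 80% holds only if all doses work equally. That needs the within-dose reading of the SD, which 10.4.2 does not state. The SD of the changes that the test analyses is a natural reading too, and under it the figure holds (step 4). Against that, the same paragraph uses one undifferentiated unit for the single-dose figure, where the SD can only be within-dose. The text leaves the question open.
- A reader might infer that an effect confined to the highest dose would be missed. The supplemental cohort tests have 99.4% power in the most extreme pattern and 85% at 1.008 SD, and dose-response models are planned as well. These tests are supplemental and unadjusted, but they are in the plan. They help less when the effect is shared by two doses (62% at 0.756 SD).
- A reader might infer that 0.3 mg/kg is expected to do nothing. The Dose Rationale compares it with tumour efficacy, not with CD8+ responses. Section 2.2 also reports apparent HIV-specific responses in two of six participants after a single 0.3 mg/kg dose of an anti-PD-L1 antibody, and average plateau receptor occupancy of 72% (range 59% to 81%) with nivolumab at 0.3 to 10 mg/kg. The lack of a clear dose response above 1 mg/kg also argues against the steepest patterns.

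Two more points stand. Dilution is the larger threat and needs a different answer (step 5). The stratified test also pools variances across cohorts: with no effect and cohort SDs in the ratio 1:2:4, simulated type I error is about 5.7%.

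It can also be said that such refinements belong in the statistical analysis plan. But the protocol has already fixed the test and its power statement, so the change has to be made against that text.

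**Conclusion.** The point holds as a modest inefficiency and an unclear unit. The pooled test puts between-dose differences into its error, and 10.4.2 does not say which SD it means or that its effect is an average over doses. If the SD is within-dose and the average change stays at 0.504, the loss is about 1 point for a mild gradient, 4 to 5 points if 0.3 mg/kg is inert, and 15 points only if one dose carries everything. If the SD is total, the stated power stands. These sizes rest on assumed dose patterns, normal changes, equal variances and 11 evaluable per cohort. The stated power contains no calculation error, type I error of the pooled test is sound, and the outcome is secondary.

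**What to change.** **In 10.6.2**, replace the pooled paired t-test by a linear model of within-person change with dose cohort as a fixed factor. Test the average of the three cohort mean changes, weighted by evaluable number, using the within-cohort error (30 df with 11 per cohort). That average is the same quantity the pooled test estimates. Keep the supplemental per-cohort tests.

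**In 10.4.2**, state that 0.504 is in within-cohort SD units and is the average change over the three doses, so that inactive doses dilute it. With 30 df the power at 0.504 is 80.0%, so the text should then say about 80%.

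**Cost:** a sentence in each section and no new data. Two error degrees of freedom are lost (about 0.2 power points if doses are equal), and type I error rises slightly if cohort variances differ greatly.

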## 10.7 Unblinding

For unblinding requests, including emergency unblinding, refer to ACTG Standard Operating Procedure (SOP)-123, Unblinding Participants, (<https://member.actgnetwork.org/cms/folder/6184>).

In the event that emergency disclosure of treatment assignment is thought to be required, the site investigator must follow ACTG SOP- 123, Unblinding Participants.

- (1) Sudden (or unplanned) unblinding of one or more arms due to interim analysis results or results of another trial: The decision to unblind one or more arms of an ongoing study is made by the team in conjunction with the relevant Scientific Committee and the Executive Committee. This can occur based on a recommendation from the DSMB or an SMC or the results of another trial (also see the DAIDS SOP “Termination of a Trial or a Single Treatment Arm”).
- (2) Participant contact: If the decision is made to unblind, participants should be unblinded as soon as possible. Unblinding is conducted through the DMC, which sends treatment assignments to the sites soon after the unblinding decision. Every effort should be made by the sites to contact participants who have completed follow-up in order to explain the study results.
- (3) Implications of unblinding on study data: When a treatment comparison is unblinded based on an interim analysis, the results of that interim analysis must be reported in publications. Data from visits that occurred before the interim review but that were not in the database at the data cutoff date have little potential for bias and may be reported with a comment. Data from visits that occurred after unblinding are potentially biased and must not be used if the intent is to claim that all the data are from a blinded study. In unblinding due to both “interim analysis” and the “other trial results” situations, if analyses are reported on clinical data or samples taken after the unblinding date, the conditions under which these data were gathered must be made clear in any publication.

Unblinding will not occur to allow replacement of participants (see [section 6.2.5](#)). Premature treatment discontinuation, other than for a treatment-related AE, would result in an increase in the applicable limit for enrollment into the active or placebo arm (as appropriate) for the designated cohort by the ACTG randomization department.

All site e-mails to the team should be carefully worded to prevent unblinding the team, if possible.

Unblinding of all study participants will take place after the last participant has completed the study, all data have been entered into the database and cleaned for primary and secondary endpoints.

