#### 6.2.5 Discontinuation Evaluations

Evaluations for Randomized Participants Who Do Not Start Study Treatment

Participants who withdraw from the study prior to starting study treatment/placebo should have entry/day 0 and off-study forms completed and keyed. No further evaluations or follow-up are required for these participants. Participants will be replaced. All eCRFs must be completed for the period up to and including entry/day 0.

Premature Treatment/Placebo Discontinuation Evaluations

Participants who begin but do not complete of both infusions of cemiplimab/placebo, but receive some of the investigational product, and are willing to stay on the study, will be followed for safety by completing all study visits and evaluations as outlined in the SOE. If one or both cemiplimab/placebo infusions have been administered, samples for serum cemiplimab, RO, and ADA will be collected per the SOE (duration of sampling in participants that do not receive or complete the second infusion will be decided on a case-by-case basis with the core team). Whether virologic, immunologic, and stored ARV plasma samples will be stored or performed following premature discontinuation of cemiplimab/placebo infusions will be determined on a case-by-case basis in discussion with the core team. The duration of the infusion (including actual start and stop times) and the volume of each cemiplimab/placebo infusion should be recorded. Participants who do not complete  $\geq 90\%$  of both infusions of cemiplimab/placebo will be replaced unless the participant has reached a protocol-defined safety endpoint. Participants who withdraw should be explicitly asked about the contribution of possible AEs to their decision to withdraw consent, and any AE information elicited should be documented.

Discontinuation of Antiretroviral Therapy

Participants who discontinue cART for any reason will be followed for safety by completing all study visits and evaluations as outlined in the SOE. If ART is discontinued prior to completion of cemiplimab/placebo infusions, then no further infusions should be given. Whether cemiplimab serum concentrations or RO assays will be collected following discontinuation of ART will be determined on a case-by-case basis in discussion with the core team. Stored plasma/PBMC for

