#### Premature Study Discontinuation Evaluations

Participants who prematurely discontinue study participation after completing one or more of the cemiplimab/placebo infusions will have the premature study discontinuation (D/C visit) evaluations performed per the SOE. Participants who discontinue the study prior to week 12 without having met the primary safety outcome measure will be replaced.

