#### 10.2.1 Primary Outcome Measures

##### 10.2.1.1 Safety

Occurrence of a Grade  $\geq 3$  AE, or Grade  $\geq 1$  irAE (such as, but not limited to, pneumonitis, colitis, adrenal insufficiency, or hypothyroidism), that is related to study treatment (as judged by the

core team, blinded to treatment arm) any time from study treatment administration through the week 48 visit.

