### 10.4 Sample Size and Accrual

The total sample size of this study is 45 evaluable participants. Within each dose cohort, there will be 12 active-treated participants and 3 placebo participants. Ultimately, there will be a total of nine placebo recipients for comparison of immunologic and virologic outcomes. Participants who do not receive study treatment will be replaced. In addition, any participant who does not receive  $\geq 90\%$  of both study treatment infusions, or discontinues the study prior to week 12 without having met the primary safety endpoint ([section 10.2.1.1](#)), will be replaced.

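### Section 10.7 ties replacement to a different exception (stops for a treatment-related AE) from sections 6.2.5 and 10.4 (the primary safety endpoint), so some participants get opposite answers

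*Protocol*

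**What the plan says.** The protocol describes replacement in three places.

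- **Section 6.2.5**, on participants who receive less than 90% "of both infusions of cemiplimab/placebo will be replaced unless the participant has reached a protocol-defined safety endpoint". For those who leave the study early it adds: "Participants who discontinue the study prior to week 12 without having met the primary safety outcome measure will be replaced".
- **Section 10.4** repeats the 90% condition, extends replacement to anyone who "discontinues the study prior to week 12 without having met the primary safety endpoint", and points to 10.2.1.1 for that endpoint.
- **Section 10.7** says that the blind will not be broken to allow replacement, refers to 6.2.5, and then describes how the randomization department opens a slot: "Premature treatment discontinuation, other than for a treatment-related AE, would result in an increase in the applicable limit for enrollment".

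The endpoint in 10.2.1.1 is a Grade 3 or higher AE, or a Grade 1 or higher "irAE (such as, but not limited to, pneumonitis, colitis, adrenal insufficiency, or hypothyroidism), that is related to study treatment (as judged by the" blinded core team, through week 48. A related Grade 1-2 AE that is not an irAE does not meet it.

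Two other sections determine the consequence. Section 10.6.2 limits efficacy analyses to participants who completed at least 90% of both infusions. Section 10.4.2 bases per-dose power on this premise: "With 11 evaluable treated participants in a dose group (allowing for one unevaluable, e.g., due to issues with the sample or assay".

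**The concern.** The exception in 10.7 has no grade limit and no irAE limit, and it does not say who judges relatedness. The exception in 6.2.5 and 10.4 is the blinded core team's primary endpoint. These are different sets of participants. Section 10.7 is also the only text on how an arm's limit is raised under the blind, so a reader carrying out a replacement would look there.

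If 10.7 is followed literally, a slot that 10.4 promises to fill can stay empty. The participant concerned is also outside the efficacy set, so the evaluable number in a dose group falls. The primary safety analysis loses nobody, because 10.6.1 includes everyone exposed. What is at stake is the power of the secondary CD8+ T cell analysis, and having one replacement rule that sites, the core team and the randomization department all apply in the same way.

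**Working it through.** **1. The rules side by side**

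| Participant | 6.2.5 and 10.4 | 10.7 |
|---|---|---|
| Stops for a related Grade 3+ AE or a related irAE | not replaced | limit not raised |
| Stops for an unrelated reason, endpoint not met | replaced | limit raised |
| Stops for a related Grade 1-2 AE, not an irAE | replaced | by implication, limit not raised |
| Met the endpoint, but stopped for another reason | not replaced | limit raised |
| Completes both infusions, leaves before week 12, endpoint not met | replaced | not mentioned |

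The first two rows agree. The third and fourth contradict each other, and the fifth is a gap in 10.7. The table reads the exception in 10.4 as covering incomplete infusions as well as early withdrawal, as 6.2.5 does. If it covered early withdrawal only, 10.4 would replace more people and stand further from 10.7.

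**2. Whether the third row can occur**

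Section 8.1.1 treats related Grade 1-2 events that are not possible irAEs as a separate category. Section 8.2.2 stops an infusion for a Grade 2 reaction and leaves resumption to the investigator. Section 9.1 lists drug-related toxicity as a reason to end treatment, with no grade in that line. The protocol therefore foresees such events, but gives no rate at which they end treatment.

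**3. The stated power**

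Inputs from 10.4.2: paired t-test, two-sided alpha 0.05, n=11 at d=0.94 SD, and pooled n=33 at d=0.504 SD. With T a noncentral t variable on n-1 degrees of freedom and noncentrality d√n, power = P(|T| > critical value).

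- n=11: noncentrality 0.94 × √11 = 3.12, power 80.2%.
- n=33: noncentrality 0.504 × √33 = 2.90, power 80.2%.

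Both reproduce the stated figure of more than 80%.

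**4. Power when slots stay empty**

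Per dose group, starting from 12 active participants, at 0.94 SD:

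| Losses | Evaluable n | Power |
|---|---|---|
| One unreplaced stop, no assay loss | 12 - 1 = 11 | 80.2% |
| Two unreplaced stops, or one plus the assay loss | 12 - 2 = 10 | 75.4% |
| Two unreplaced stops plus the assay loss | 12 - 3 = 9 | 69.6% |

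The effect detectable with 80% power rises from 0.94 SD at n=11 to 1.00 SD at n=10 and 1.07 SD at n=9.

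Pooled, at 0.504 SD, starting from 36 active participants with three losses already allowed: n=33 80.2%; n=32 (one further loss) 78.9%; n=30 (three further losses) 76.1%.

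**5. How often two stops would occur in one dose group**

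No rate is given, so q, the chance per participant of an unreplaced stop, is an assumption. P(at least 2 of 12) = 1 - (1-q)^12 - 12q(1-q)^11.

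| Assumed q | P(at least 2 of 12) |
|---|---|
| 2% | 2% |
| 5% | 12% |
| 10% | 34% |
| 20% | 73% |

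Because the disputed group is narrow, the upper rows are a bound and not an expectation.

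**The case against.** The strongest reply is that 10.7 is an unblinding section and not the replacement rule. It refers to 6.2.5 and then describes a mechanism. That is fair as far as precedence goes: nothing in the protocol says that 10.7 overrides 6.2.5 and 10.4, or that the randomization department would follow it in preference to them. But 10.7 goes on to state a different exception, and a cross-reference does not reconcile two different conditions.

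Several stronger readings are tempting, and the protocol does not support them.

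- *Section 10.7 bars replacement after any treatment-related AE.* It states only what raises the limit. The bar is implied, and it applies only when treatment stops for that AE.
- *Mild infusion reactions will regularly trigger the conflict.* Under 8.2.1 a Grade 1 reaction does not call for interruption, and under 8.2.2 a Grade 2 infusion may be resumed. Section 7.2 can also be read as counting Grade 2 or higher infusion reactions among irAEs. Section 10.4.1 B excludes infusion reactions from its irAE criterion, whereas 10.2.1.1 has no such exclusion. On that reading the two rules agree for those events.
- *The oncology data show how many slots would be lost.* In section 2.2, 512 of 757 patients had a related AE, 339 a potential irAE, 96 a related Grade 3+ AE and 63 a Grade 3+ potential irAE. Potential irAEs were drawn from the related AEs. So 512 - 339 = 173 patients (22.9%) had a related AE and no potential irAE. At most 96 - 63 = 33 of them had a Grade 3+ event, which leaves 140 to 173 patients (18.5% to 22.9%) with neither. This is AE incidence in cancer patients, some on combination therapy. It is not a rate of stopping after one of two infusions.

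Two further points on the other side stand. The omission of week 12 from 10.7 is a gap and not a contradiction, since 6.2.5 and 10.4 cover it. The per-dose tests are supplemental, and the outcome is secondary.

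**Conclusion.** The passages conflict and must be reconciled. They give opposite answers for a participant who stops for a related Grade 1-2 AE that is not an irAE, and for one who met the endpoint but stopped for another reason.

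The practical effect is probably small. One unreplaced stop on its own costs nothing against the stated power. It takes two in the same dose group, or one together with the allowed assay loss, to bring per-dose power to 75.4%. The main pooled test loses 1.3 percentage points for one loss beyond the three allowed (80.2 - 78.9) and 4.1 points for three (80.2 - 76.1). These figures assume the protocol's own effect sizes and the exact paired t-test. The frequency of such stops is unknown.

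A reader might infer that aligning the sections would protect n=11. It would not do so fully. Participants who stop treatment because of a true safety endpoint are unreplaced under either rule, and those without 90% of both infusions are excluded from efficacy. The evaluable number can fall below 11 by that route whichever wording is used.

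**What to change.** Make the trigger in 10.7 the same as in 6.2.5 and 10.4: the limit for the relevant arm is raised for any participant who does not receive at least 90% of both infusions, or who leaves the study before week 12, unless the primary safety endpoint in 10.2.1.1 was met. Cite 10.2.1.1 in 6.2.5 as well, so that all three sections name the same endpoint. This changes who is replaced and leaves the rules for stopping treatment untouched.

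Add one sentence to 10.4.2 stating that n=11 per dose group and n=33 pooled assume no more than one loss per cohort from all causes, including participants who stop after a safety endpoint and are not replaced.

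The cost is one reworded sentence in 10.7, a cross-reference in 6.2.5, one added sentence in 10.4.2, and an occasional extra replacement that 10.4 already provides for.
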